11.2.4 Concomitant Medication

Information on concomitant treatment will comprise all concomitant therapies at the MRE examination and until the end of treatment visit 2, blood sampling. Acceptable concomitant treatment options are described in [Section 10.1](#).

11.2.5 Assessment of Safety

AEs will be recorded from the time of informed consent (Day 0) until the follow-up visit or early termination visit.

For safety reasons, subjects will be contacted within 2 to 4 days after the MRE examination by the investigator and asked about occurrence of any adverse event. No other follow-up is planned.

Detailed instructions regarding AE handling, monitoring and reporting are provided in [Section 0](#) (Adverse Events).

11.2.6 Electrolyte assessment

Plasma potassium, sodium, phosphate, and calcium, as well as ionized calcium blood concentration levels will be monitored over 24 hours from just before (baseline) the subject starts drinking Lumentin® 44. Blood samples will be drawn at baseline (T0h), and then at 1 hour (T1h), 2 hours (T2h), 4 hours (T4h), 6 hours (T6h), 8 hours (T8h) and at 24 hours (T24h).

An IV antecubital cannula will be placed for pre-blood samples and used during the first 8h including administration of Gd during the MRE procedure. Thereafter it will be discarded. Blood sampling on the following day after (24h time point) will be drawn without a cannula.

Electrolyte blood samples will be taken, handled, and analysed according to standard procedures at the clinic. The laboratory will provide normal ranges.

11.2.7 MRE examination

Preparation before MRE: Subjects will be fasting (2 decilitres of clear water is allowed) for at least six hours prior to the MRE procedure.

The MRE-examination will take approximately 40 minutes. The MR-examination will not be performed if the subject has not been able to drink at least 1.1 L of Lumentin® 44.

Broadly, MRE is a scanning technique for creating detailed images of parts of the human body, using a strong magnetic field and radio waves. It is based on the magnetisation properties of atomic nuclei. A powerful, uniform, external magnetic field is employed to align the protons that are normally randomly oriented within the water nuclei of the body part examined. This alignment (or magnetisation) is disrupted by introduction of an

external Radio Frequency (RF) wave energy. The nuclei return to their resting alignment through various relaxation processes and in doing so emit RF energy. Tissues are characterised by two different relaxation times, of which T1, the longitudinal relaxation time, determines the rate at which excited protons return to equilibrium. It is a measure of the time taken for spinning protons to realign with the external magnetic field. The contrast and brightness of the image are predominately determined by T1 properties of tissue.

During an MRE-examination, the subject will be asked to lie prone on a movable table that will slide into a doughnut-shaped, deep opening and centred for scanning the small bowel. As part of the procedure a strong magnetic field will be generated around the subject, and pulsating radio waves will be directed at the body. Because of loud thumping and tapping noises during the scan the subject will be given headphones to listen to music or earplugs to help block the sound. The subject will be able to communicate with the technician who gives instructions during the test. The contrast agent Clariscan® (0.1 mmol/kg) and the muscle relaxant Buscopan® (40 mg) (to reduce bowel motility) will be administered IV. Clariscan and Buscopan can be replaced with comparable product according to the standardised procedures at the clinic. The specific details of the MRE-system used will be noted in the CRF.

11.3 Outcome assessments

11.3.1 Primary outcomes

All MRE images will be evaluated by one expert radiologist. Only one assessment of each MRE examination will be performed.

The primary endpoint is the visual evaluation of the MRE images according to the following parameters:

Motility: MRE examinations with Lumentin® 44 will be scored with respect to motility status based on a 5-graded scale, as follows:

1. No motility could be assessed
2. Motility is assessed to some degree but less good than conventional MRE
3. Motility is assessed to same degree as conventional MRE
4. Motility is assessed somewhat better than conventional MRE
5. Motility is assessed better than conventional MRE

Motility should be evaluated as a whole in the specific cine- sequences and resulting in one ordinal score 1-5.

Artefacts: MRE examinations with Lumentin® 44 will be scored with respect to artefacts based on a 5-graded scale, as follows:

1. Severe deteriorating artefacts in the interface between the lumen and wall
2. Disturbing artefacts in the interface between the lumen and wall less good compared to conventional MRE
3. Medium artefacts in the interface between the lumen and wall, same as for conventional MRE
4. Small artefacts that give minimal bright edges in the interface between the lumen and wall, somewhat better than conventional MRE
5. No artefacts and better than conventional MRE

Artefacts should be evaluated as a whole in all sequences and resulting in one ordinal score 1-5.

Mucosal evaluation: MRE examinations with Lumentin® 44 will be scored with respect to mucosal status based on a 5-graded scale, as follows:

1. No mucosal folds are seen
2. Some small mucosal folds can be discriminated
3. Mucosal folds can be discriminated, same as for conventional MRE
4. Small mucosal folds can be discriminated, somewhat better than for conventional MRE
5. Mucosal folds are seen in detail and better than conventional MRE

Mucosal evaluation a) coronal and b) axial T1 gradient-echo with Gd should be done and resulting in one ordinal score 1-5.

Overall diagnostic impression: MRE examinations with Lumentin® 44 will be graded for global quality of the information obtained with special reference to diagnostic purposes, as follows:

1. Poor diagnostic quality
2. Medium diagnostic quality, below conventional MRE
3. Good diagnostic quality, same as for conventional MRE
4. Very good diagnostic quality, somewhat better than conventional MRE
5. Excellent diagnostic quality, better than conventional MRE

The quality of the whole examination and what the impression is for using the examination for diagnostic purposes will be graded.

12 ADVERSE EVENTS

Any untoward medical occurrence in a subject or clinical trial subject administered a medicinal product and which does not necessarily have a causal relationship with this treatment. Untoward medical occurrences occurring prior to the MRI/ MRE assessment will not be reported as an adverse event. All AEs occurring throughout the trial will be recorded and followed.

Comment: An AE can therefore be any unfavourable and unintended sign (including an abnormal laboratory finding), symptom, or disease temporally associated with the use of an IMP, whether or not considered related to the IMP.

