	
eligible for the trial they will then visit the clinic for MRE assessment within 1-2 weeks.
 
Only the first 10 of the eligible HVs will be asked to come for MRE examination and the remaining eligible subjects will be asked to stand by in case any of the 10 subjects are unable to come or cannot undergo the examination.
 
HVs will be asked to fast for 6 hours prior to the examination on the day of the MRE examination. Clear liquid in small volumes up to 2 decilitres is allowed. Prior to MRE, Lumentin® 44 will be provided to them in volumes of up to 1.5 L and at least 1.1 L of Lumentin® 44 must be drunk. The subjects will be asked to drink the solutions of oral contrast agent within 45 minutes to 1 hour.
 
Subjects not able to drink at least 1.1 L of Lumentin® 44 will be withdrawn from the trial.
 
Prior to the intake of Lumentin® 44, an intravenous (IV) antecubital cannula will be placed and used for blood sampling and administration of Gd contrast agent during the MRE assessment.

Assessments	
Screening assessments: HVs fulfilling the eligibility criteria and who sign the consent to participate will undergo a physical examination, perform a pregnancy test (females only) and have a creatinine blood sample taken. Medical history, demographics, concomitant treatment and illnesses will also be recorded..
 
MRE assessment: MRE will start within 10 minutes after the contrast agent has been drunk and will last for approximately 40 minutes.
 
The HV will be brought to the MRE-scanner suite inside the magnet using the moving table and scanning will commence. All series will be taken as per standard clinical MRE protocol recognised by radiologists in Europe and North America. After dynamic series acquisition, a spasmolytic agent will be given and 3D gradient-echo series will be taken and will be repeated 40 seconds thereafter, following IV administration of Gd contrast agent at a dose of 0.1 mmol/kg per body weight. Subsequently, the remaining series will be taken according to protocol.

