Statistical analyses	
All subjects who have completed the trial will be included in the statistical evaluation.
 
No statistical tests will be conducted. Confidence intervals may be constructed and will then be 2-sided and of 95% confidence.
 
Continuous data will be summarised using descriptive statistics (N, mean, median, standard deviation, minimum and maximum). Categorical data will be summarised by frequency tables (numbers and percentages).
 
Unless otherwise stated, all analyses will be done on observed cases without any substitution of missing values.

Schedule of Assessments

Visit/Contact	1	2	3	4	5
	Pre-screening	Screening	MRE examination	Blood sampling	F-U ⁽¹⁾ and early termination
Day	-21 to -1	0	14	15	Visit 2 +2 days
Visit window (days)			+/- 7 days	-	+ 2
Subject information	X	X			
In/exclusion criteria	(X) ⁽²⁾	X			
Informed consent		X			
Physical examination		X			
Pregnancy test ⁽³⁾		X			
Creatinine blood sample		X			
Subject demographics (incl. height and weight)		X			
Concomitant treatment	X	X	X	X	X
Concomitant illnesses	X	X			
Medical history	X	X			
Adverse event(s) recording			X ⁽⁴⁾	X	X
Placement of IV antecubital cannula			X ⁽⁵⁾		

Visit/Contact	1	2	3	4	5
	Pre-screening	Screening	MRE examination	Blood sampling	F-U ⁽¹⁾ and early termination
Day	-21 to -1	0	14	15	Visit 2 +2 days
Visit window (days)			+/- 7 days	-	+ 2
MRE Scan			X		
Dispensing of Lumentin® 44			X		
Administration of Gd contrast (6)			X		
Administration of Buscopan® (6)			X		
Evaluation of extension and distension of bowel filling agents			X		
Blood sampling			X ⁽⁵⁾ (pre-, 1, 2, 4, 6, 8h)	X (24h)	
Compliance			X		

- 1) Subjects will be contacted by telephone two to four working days post MRE assessment.
- 2) Only some of the criteria will be checked including, inclusion criterion 1 and exclusion criteria 2, 3, 4, 5, 6, 7, 8, 12 and 13.
- 3) Urine pregnancy test of all females who are not surgically sterile (hysterectomy or tubal ligation) or postmenopausal (i.e., experienced 12 consecutive months without menstruation).
- 4) Telephone interviews will be conducted 2 days after MRE assessment to investigate if any AEs occurred during the first days after the imaging procedure
- 5) An IV antecubital cannula will be placed for pre-blood samples and used during the first 8h including administration of gadolinium during the MRE procedure. Thereafter it will be discarded. Blood sampling on the following day (24h time point) will be drawn without a cannula.

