7 OVERALL DESIGN AND PLAN OF THE TRIAL

7.1 Trial Overview

This is an uncontrolled, single centre phase II trial. Enrolled HVs (n=10) will undergo Gd-enhanced MRE after oral intake of Lumentin® 44.

Interested HVs will be identified primarily among medical students at the medical hospitals at Malmö and Lund. Posters will be placed at the departments and invitation letters will be handed out.

The HVs interested in participating will be invited to attend a pre-screening visit where their suitability based on age and health status will be assessed. Fifteen HVs who fulfil the pre-screening criteria and are interested in participating will be asked to attend a screening visit at the clinic and if eligible for the trial they will then visit the clinic for the MRE assessment within 1-2 weeks.

Only the initial 10 of the eligible HVs will be asked to come for the MRE examination and the remaining eligible subjects will be asked to stand by in case any of the 10 subjects are unable to come or cannot undergo the examination.

HVs will be asked to fast for 6 hours prior to the examination on the day of the MRE examination. Small amount of clear liquid is allowed up to 2 decilitres. Prior to MRE, Lumentin® 44 will be provided to them in volumes of up to 1,500 mL and at least 1,100 mL of Lumentin® 44 must be drunk. The subjects will be asked to drink the solutions of oral contrast agent within 45 minutes to 1 hour.

Subjects not able to drink at least 1.1 L of Lumentin® 44 will be withdrawn from the trial.

Prior to the intake of Lumentin® 44, an IV antecubital cannula will be placed and used for blood sampling and administration of gadolinium (Gd) contrast agent during the MRE assessment.

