12.2 Reporting of Adverse Events

All trial subjects will be carefully monitored for the occurrence of AEs during the trial period, from start of intake of the first dose of contrast agent until the follow-up visit. Also, telephone interviews will be made 2 days after MRE assessment to investigate if any AEs occurred during the first days after the examination. Any pregnancies occurring in the same trial period will be reported and followed.

Reported AEs will be followed up (see [Section 12.5](#) below). The Investigator will collect AEs with a non-leading question such as “have you experienced any new health problems or worsening of existing conditions” as well as reporting events directly observed or spontaneously volunteered by subjects.

Clearly related signs, symptoms and abnormal diagnostic procedure results should be grouped together and reported as a single diagnosis or syndrome whenever possible.

All AEs including but not limited to events reported by the subject, or reported in answer to an open question by the Investigator or member of this team, which fall into any of the above definitions must be recorded as an AE in the CRF and should include the following information:

- Brief description of the event (diagnosis)
- Start date (and time, if relevant)
- Stop date (and time, if relevant)
- Severity
- Action taken regarding trial treatment
- Opinion on causality
- Seriousness
- Outcome

AEs will be coded with Medical Dictionary for Regulatory Activities (MedDRA), the version of which will be provided in the trial report.

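### No planned analysis has to count a subject who is withdrawn and replaced because of an AE during drinking; the start of AE recording is also stated in three ways

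*Combined protocol and SAP*

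**What the plan says.** **Withdrawal and replacement.** Section 9.2 stops intake when an AE occurs and withdraws a subject whose intake has to be stopped; 8.3.1 says the same. Section 8.3.2 makes withdrawal mandatory for anyone who cannot drink 1.1 L, but lists AEs in general among the discretionary reasons. Section 11.2.7 bars the scan below 1.1 L. Under 8.3.2 a subject withdrawn without an evaluable scan is replaced, and an Early Termination page is completed for anyone withdrawn after receiving the product.

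**Analysis.** The synopsis puts subjects who completed the trial into the statistical evaluation; 13.3 says those who fulfilled it. Section 13.4 summarises collected data without naming a population. Section 13.5 leaves exclusions to a clean file meeting and gives no criteria. No safety set is named. TEAE is expanded in the abbreviation list but has no onset rule.

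**Start of AE recording.**
- Section 11.2.5: "AEs will be recorded from the time of informed consent (Day 0) until the follow-up visit or early termination visit".
- Section 12.2: "from start of intake of the first dose of contrast agent until the follow-up visit".
- Section 12: "Untoward medical occurrences occurring prior to the MRI/ MRE assessment will not be reported as an adverse event", followed at once by "All AEs occurring throughout the trial will be recorded and followed".

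**The concern.** The product is drunk in a large volume over a short time, so intolerance during drinking is central to the safety and tolerability objective (6.2) and its TEAE and TEADR outcome (7.2.2). The withdrawal, replacement and analysis rules together can take exactly those subjects out of the summary: the subject who could not tolerate the foam leaves, a standby subject who can tolerate it takes the place, and the named population consists of those who finished. The reported TEAE rate would then describe people selected for tolerance.

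The wording on when AE recording starts raises a second, smaller question. Depending on what the MRE assessment means in section 12, an event during drinking might not be classed as an AE at all.

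**Working it through.** The plan has no figure to reproduce: 13.2 says that the 10 subjects are not based on a calculation. The check is mainly a comparison of passages.

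**1. Following a subject with an AE during drinking.**
- *Less than 1.1 L drunk.* Intake stops (9.2). Withdrawal is mandatory on volume alone (7.1, 8.3.2, 9.2), so the discretionary listing of AEs in 8.3.2 does not help. There is no scan (11.2.7), and the subject is replaced (8.3.2). The subject has neither completed nor fulfilled the trial.
- *At least 1.1 L drunk.* Sections 9.2 and 8.3.1 still withdraw the subject once intake has to be stopped, while 8.3.2 lists AEs as discretionary. Section 11.2.7 does not bar the scan. The subject may be scanned, not replaced, and counted. The outcome depends on which wording the site follows.
- *Either case.* The AE can be on the CRF, but neither the synopsis nor 13.3 or 13.4 requires any summary to include a subject who did not finish.

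**2. Illustration of size.** Let k be the number of subjects whose intake is stopped for an AE and who are replaced, with every replacement finishing. The number dosed is 10 + k and the true proportion is k/(10 + k). Among finishers the count is 0 of 10. Exact (Clopper-Pearson) 95% limits for x of n are the 0.025 quantile of Beta(x, n − x + 1) and the 0.975 quantile of Beta(x + 1, n − x).
- Finishers only: 0/10 = 0%; upper limit 1 − 0.025^(1/10) = 30.8%.
- k = 1: 1/11 = 9.1% (0.2 to 41.3%).
- k = 2: 2/12 = 16.7% (2.1 to 48.4%).
- k = 5, all five standby subjects used: 5/15 = 33.3% (11.8 to 61.6%).

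These values of k are assumed.

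**3. The three starts.**
- *Consent against the MRE visit.* The Schedule puts the MRE visit at Day 14 ± 7, so these starts differ by 14 − 7 = 7 to 14 + 7 = 21 days, all before dosing.
- *Section 12 read as the visit.* Section 7.1 uses the term this way: "they will then visit the clinic for the MRE assessment within 1-2 weeks". The sentence then nearly coincides with first intake (12.2) and conflicts with consent (11.2.5).
- *Section 12 read as the scan.* The synopsis uses the term this way: "MRE assessment: MRE will start within 10 minutes after the contrast agent has been drunk and will last for approximately 40 minutes". Section 7.1 places drinking before it: "Prior to MRE, Lumentin® 44 will be provided to them in volumes of up to 1,500 mL". Schedule footnote 4 ties it to imaging: "2 days after MRE assessment to investigate if any AEs occurred during the first days after the imaging procedure". The excluded period is then drinking time plus the wait. With 30 to 60 minutes (9.2) plus 0 to 10 minutes (synopsis), that is 30 to 70 minutes; with the 1½-hour limit also in 9.2, up to 90 + 10 = 100 minutes.

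**The case against.** The strongest reply is that the plan is silent rather than exclusive. Neither 13.3 nor the synopsis says that only finishers are analysed, 13.4 summarises collected data, 7.2.2 covers any TEAE, 11.3.2 collects all AEs, and the Early Termination page keeps the record. This stands as far as it goes. A reader might infer that the plan discards these subjects' data or forbids counting them; the documents do not support that. But keeping data does not set a denominator, and the only population named points to finishers.

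The path is also narrower than every AE during drinking. After 1.1 L the subject may be scanned and counted. It can further be argued that 8.3.1 concerns stopping the product and 8.3.2 leaving the trial, so the two need not clash. That limits the claim to subjects who do not finish. It does not rescue those stopped below 1.1 L.

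On the start rules, a reader might infer that section 12 removes AEs during drinking from the trial. The balance of the text is against this: the synopsis records AEs for the whole trial, 11.1.3 and the Schedule list AE recording at the MRE visit, 12.2 starts at first intake, and section 12's own next sentence covers all AEs. SAE reporting under 12.5 is not removed on any reading. On the visit reading, what remains concerns pre-dose events, which cannot bias a treatment-emergent outcome.

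Nor is there an expected frequency. The AE rates from earlier trials in 7.3.1 give neither onset relative to drinking nor whether intake was stopped.

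**Conclusion.** The main point holds: a subject stopped by an AE during drinking, certainly one below 1.1 L, is withdrawn and replaced, and no planned analysis must include that subject. The TEAE outcome can therefore understate intolerance. The size is unknown. One such subject would be 1 of 11 dosed (9.1%) and could be shown as 0 of 10. The wide, overlapping intervals show that a trial this small could not reveal the loss from its own results. The point assumes that at least one such event occurs and that the summary is run on finishers, which the plan permits but does not order.

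The secondary point holds as an inconsistency in wording. It would affect the TEAE result only on the scan reading, which is the less supported one. The sentence in section 12 should still not stand, because its literal meaning could remove the drinking period. The primary image endpoint is not affected.

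**What to change.** - In 13.3 and the synopsis, add a safety set of all subjects who took any Lumentin 44, including those withdrawn or replaced. Report TEAEs and TEADRs on it with its own denominator. Membership then follows from intake and is not left to the clean file meeting.
- Define a TEAE as an event with onset at or after first intake, and list earlier recorded events separately.
- Delete the exclusion sentence in section 12. State one start of AE recording, no later than first intake, in 11.2.5, 12, 12.2 and the Schedule. If consent is kept as the start, add AE recording at Visit 2 in 11.1.2 and the Schedule.

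The sponsor should also reconcile, as housekeeping, the wording on withdrawal for AEs (8.3.1, 8.3.2, 9.2), the intake time limits (synopsis, 7.1, 9.2), and the anchor and window of Visit 5 (Schedule, 8.4, 11.1.5, 11.2.5). No clinical rule is proposed here.

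The cost is wording, the CRF instruction for AEs and one AE summary on all dosed subjects, with no added visits or procedures. The downside for the sponsor is that the reported TEAE rate may be higher and its denominator may exceed 10.

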12.1.1 Adverse Reaction

All untoward and unintended responses to an investigational medicinal product related to any dose administered.

Comment: All AEs judged by either the reporting Investigator or the Sponsor as having a reasonable causal relationship to a medicinal product qualify as adverse reactions. The expression reasonable causal relationship means to convey in general that there is evidence or argument to suggest a causal relationship.

